#### **h. Eligibility Criteria**

##### **i. Inclusion Criteria**

- Parents or guardians  $\geq$  18 years of age
- involved in the care of a child 5-17 years old with or without bladder problems
- English speaking

##### **ii. Exclusion Criteria**

- Individuals  $<18$  years old.
- Does not meet inclusion criteria

---

#### **i. Screening Procedures**

We are recruiting by advertising our flyer and recruitment messages on virtual platforms, such as e-newsletters. On these flyers, we tell interested participants to contact us at our lab email. Flyers will also be posted in the clinic or around campus, in pediatrician offices within the Stanford network, on our lab website, and on the Stanford research websites such as those listing current research and Urology clinic website/webpage in Stanford Children's Hospital.

We are also recruiting using the honest broker system at Stanford – through MyChart messages and Direct Email.

We will contact patients via phone to assess interest, with permission from their provider to cite them as a referral so that patients understand where we obtained their information.

We will use social media to recruit potential participants

Parents may also be approached to be a part of the study at the time of referral to the clinic.

Lastly, we may use the patient access service center (PASC) to recruit participants and offer our study to patients who are waiting to be seen for their first visit at LPCH (Bladder Bootcamp or new patient visit). In terms of using PASC, we may ask PASC to direct patients to our website to learn more about our study or ask patients if it is okay for our research team to contact them about the study.

Once they express interest from the above recruitment methods, we send them the link to a REDcap web questionnaire (screening survey) to determine their eligibility for the study. If they meet all the inclusion criteria, they can proceed to complete an electronic consent form, also through REDcap. If they meet the exclusion criteria, they will be informed not to proceed with the study but can leave their contact information for future

study opportunities. Further questions may be asked by research personnel via email/call. The consent form will be administered through REDcap as a form – participants are asked to read the form and provide an electronic signature at the end of the consent form on REDcap. Once we have their consent, we proceed with sending the REDCap pre and post survey.

---

**j. Payments to Participants**

Participants will receive up to [REDACTED] Amazon gift card via email upon completion of the study, as follows:

- 1) Receive [REDACTED] after completing the pre-intervention survey, post-lesson surveys, and post-intervention survey at  $\leq$  4 weeks.
- 2) Then receive [REDACTED] after completing the post-intervention survey at 3 months.

After enrollment, if participants are found to be a repeat participant, have previously enrolled in the study, or have failed to follow study procedures, we will withdraw them from the study. Furthermore, we will stop sending the 4-week and 3-month follow-up survey and will not be able to receive [REDACTED] Amazon gift card. If participants have already been sent the 4-week survey we will proceed with not sending them the 3-month survey and will not receive the [REDACTED] Amazon gift card.

Participants will be notified on their withdrawal via e-mail and access to the Bladder Basics curriculum will be removed.

---

**k. Costs to Participants**

None

---

**l. Planned Duration of the Study**

The probable duration of the study will be 5 years.

- i) Participant screening will take approximately 5 minutes.
- ii) The total Bladder Basics viewing time is 1 hour, and participants will have 4 weeks to complete their viewing. We will provide pre-intervention and post-lesson surveys before and during the viewing. We will also provide post-intervention surveys at 4 weeks and 3 months.
- iii) Data analysis will occur concurrently with data collection.

---

**5. RISKS**

---

**a. Potential Risks**

i. Physical well-being

We do not anticipate that this study will directly impact the physical well-being of study participants.

ii. Psychological well-being

We do not anticipate that this study will directly impact the psychological well-being of study participants.

iii. Economic well-being

We do not anticipate that this study will impact the economic well-being of study participants.

iv. Social well-being

We do not anticipate that this study will impact the social well-being of study participants.

v. Overall evaluation of risk

Low

---

**b. International Research Risk Procedures**

N/A

---

**c. Procedures to Minimize Risk**

The only potential risk to participants is breach of confidentiality. All Stanford data and documents will be kept in de-identified Stanford encrypted and HIPAA compliant files in password protected data bases and be transmitted with encrypted and secure servers meeting the requisite Stanford guidelines.

---

**d. Study Conclusion**

The study will end after data has been collected. We do not anticipate any adverse events related to the study.

---

**6. BENEFITS**

We do not anticipate any direct benefits to participants in this study. The study results may help improve health education experiences of other parents and their children with bladder health issues.

---

**7. PRIVACY AND CONFIDENTIALITY**

All participant information and specimens are handled in compliance with the Health Insurance Portability and Accountability Act (HIPAA) and privacy policies of Stanford University, Stanford Health Care, and Stanford Children's Health.

# Impact, Feasibility, and Acceptability of a Digital Health Intervention for Healthy Children With Pediatric Lower Urinary Tract Symptoms (pLUTS)

## Statistical Analysis Plan

NCT05852353

July 14, 2025

Planned sample size was 100 enrolled parent-child dyads. The final sample included 70 parent-child dyads.

Feasibility metrics, secondary outcomes, and sociodemographic data were analyzed descriptively. For both the overall group and sub-groups, the following statistics will be calculated: count, percentage, mean scores, standard deviation (SD), median scores, interquartile range (IQR), minimum and maximum scores.

Paired t-tests were used for normally distributed variables, while non-parametric tests were used (Wilcoxon and Sign) for non-normally distributed variables to compare pre- and post- intervention scores. McNemar's test was used for categorical variables to evaluate changes in proportions from baseline to post-intervention.

Missing data was addressed using complete-case analysis; participants were only included if they completed the surveys specific to each post-intervention timepoint.

Statistical significance was set at  $p < 0.05$ , and analyses were conducted using R.

The reliability of the survey measuring acceptability and education design was assessed using Cronbach's alpha with an  $\alpha \geq 0.6$  and  $\leq 0.8$  considered acceptable internal consistency. Bar charts were generated to visualize the distribution of Likert scale responses, offering further insight into response patterns and helping to further explain the reliability test results.

A hybrid process combining inductive and deductive thematic analysis, guided by the theoretical framework of acceptability, was performed by two research team members to analyze open-ended feedback on families' experiences and perceptions of Bladder Basics. SPSS and Dedoose were used for statistical and thematic analyses, respectively.

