### b. Objectives

This study aims to evaluate the impacts of Bladder Basics on knowledge improvement and clinical symptoms, as well as its acceptability and feasibility through pre-intervention, post-lesson, and post-intervention surveys.

---

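### Does the SAP leave open which pre-post p-values count, and which test and package produced them?

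*SAP*

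**What the plan says.** The whole analysis plan is one page. Five statements bear on this point.

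- Description: "Feasibility metrics, secondary outcomes, and sociodemographic data were analyzed descriptively".
- Tests of scores before and after the intervention: "Paired t-tests were used for normally distributed variables, while non-parametric tests were used (Wilcoxon and Sign) for non-normally distributed variables".
- Tests of proportions: "McNemar's test was used for categorical variables to evaluate changes in proportions from baseline to post-intervention".
- Who enters each comparison: "participants were only included if they completed the surveys specific to each post-intervention timepoint".
- Software: in the sentence that sets the 0.05 threshold, "analyses were conducted using R"; in the closing paragraph on qualitative work, "SPSS and Dedoose were used for statistical and thematic analyses, respectively".

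On sample size the SAP reports that "The final sample included 70 parent-child dyads", against 100 planned. The Protocol (1b, Objectives) aims to "evaluate the impacts of Bladder Basics on knowledge improvement and clinical symptoms, as well as its acceptability and feasibility". Protocol 2a (Procedures) gives knowledge, child symptom scores and self-efficacy as examples of baseline measures, and schedules post-intervention surveys at 4 weeks and 3 months. Neither document names a primary outcome, lists the tested variables, singles out a timepoint or gives a multiplicity rule.

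**The concern.** A reader who wants to know what a significant result means meets three open questions. First, outcomes said to be only described might be among those tested, and nothing says how many tests were run. Second, Wilcoxon and Sign are both assigned to non-normal variables, so an analyst could in principle run both and report the more favourable. When changes are skewed, the two tests address different quantities. Third, two packages are credited with the statistical analyses, so the exact version of a test is not fixed.

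The documents describe no control group, so a pre-post p-value is the main quantitative evidence of impact. If its status were truly arbitrary, a chance finding could be read as an effect of the programme.

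**Working it through.** The plan gives one error-rate figure, the 0.05 threshold. It gives no power, effect size or SD, so there is no derived figure to reproduce. The calculations below are illustrations on stated assumptions (two-sided tests).

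**1. Description against testing.** The first statement covers feasibility metrics, secondary outcomes and sociodemographic data. It does not mention primary outcomes. If the tested scores are primary, both sentences hold. A contradiction arises only if a tested score is secondary, and the documents do not say that any is.

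**2. Number of tests.** For k independent tests with no true change, the chance of at least one p < 0.05 is 1 - 0.95^k:

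- k = 2: 9.75%
- k = 4: 18.5%
- k = 6: 26.5%

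Changes at 4 weeks and 3 months share a baseline. With equal correlation ρ over visits, each change has variance 2σ²(1 - ρ) and their covariance is σ²(1 - ρ), so they correlate at 0.5. A first-order autoregressive pattern gives √(1 + r)/2, which is 0.57 at r = 0.3 and 0.69 at r = 0.9. Simulation with correlations of 0.5-0.7 gives:

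- one score at two visits: 8.3-9.3%
- two scores at two visits: 15.1-17.5%
- three scores at two visits: 20.2-24.8%

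These figures rest on the assumed k. Protocol 2a offers its three measures as examples and does not give the content of the follow-up surveys, so six is neither a minimum nor a maximum.

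**3. Wilcoxon against Sign, no effect.** If nothing changes, pre and post values are exchangeable and their difference is symmetric about zero, whatever the shape of the scores. Both tests are then valid. Simulation at n = 70 with 4,000 runs gives these rejection rates:

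| Differences | Wilcoxon | Sign | Either |
|---|---|---|---|
| Normal | 4.2% | 3.7% | 5.8% |
| Laplace | 4.7% | 4.3% | 6.5% |
| Integers -3 to 3 | 5.2% | 3.4% | 6.6% |

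The last column is the direct cost of always reporting the more favourable test: at most 1.6 points above 5%. The simulation error is about √(0.06 × 0.94/4000) = 0.4 points.

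**4. Wilcoxon against Sign, true change.** With a normal shift of 0.3 SD at n = 70, Wilcoxon rejects in 67.8%, Sign in 48.7%, and at least one in 69.5%.

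- Wilcoxon alone: 69.5 - 48.7 = 20.8%
- Sign alone: 69.5 - 67.8 = 1.7%

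Of the roughly 22.5% of runs in which they disagree, about 92% (20.8/22.5) are a real change that Sign misses.

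**5. Skewed changes.** With exponential changes centred at zero median, Wilcoxon rejects in 28% and Sign in 4%. Such changes have mean 1 - ln 2 = 0.31 above zero, so the distribution has moved and the Wilcoxon rejections are not plainly errors. The documents give no evidence of skew of this kind.

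**6. Software.** The sentence that sets the threshold is the one that names R. SPSS is named in the closing paragraph on thematic analysis, directly after the paragraph on reliability. Switching the Wilcoxon continuity correction on or off changed the verdict in 0.03% of runs. Other options matter more: handling of zero differences changes it in 1.0-6.4%, and exact against uncorrected McNemar in 2.0-11.1%. Those figures compare options within a method. They do not show that R and SPSS differ.

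**The case for a change.** The strongest case for a change is that a plan should let a reader count the tests and know beforehand which result will be reported, and this one does not. The gap between Wilcoxon and Sign is the most substantial part. On bounded integer scores with changes of 0.22-0.33 SD, the tests fall on different sides of 0.05 in 12.9-17.8% of simulated data sets. With skewed changes of zero mean, Wilcoxon rejects in 9-29% and Sign in 11-58%. A reader who takes significance to mean a shift in the average could then be misled.

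Part of this stands. The tested outcomes are not listed, no choice rule is written down, and the two software sentences do not agree. A report that gave a p-value without naming its test would be hard to interpret.

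The rest does not carry the point to a fault in the plan. Disagreement means one p-value below 0.05 and one above, not effects in opposite directions, and under a true change it mostly reflects the lower power of Sign. In the zero-mean case the median is not zero, so rejections by Sign are correct for the quantity it tests. The lack of a control group limits causal reading however the tests are listed. Finally, the SAP is written mostly in the past tense and reports the final sample: a rule added now would record what was done, but could not make any p-value prespecified.

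**Conclusion.** No change to the plan is needed. What is missing is detail that analysts supply as a matter of course when they name the outcome, the timepoint and the test beside each p-value. The conflict between R and SPSS is a clerical slip. Whether to call the p-values exploratory is a reporting convention in an uncontrolled, low-risk education study with feasibility and acceptability among its aims, and the documents claim no confirmatory test.

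The size that can be supported is small: with no effect, free choice between the two non-parametric tests raises the error rate for one comparison from 5% to at most about 6.6%. That figure assumes n = 70 and symmetric changes; complete-case numbers at each follow-up may be lower. The family-wise rates of 8-25% and the disagreement rates depend on test counts, effects and distributions that the documents do not give, so they remain illustrations. None of them shows that a stated rule yields a wrong result. The judgement would differ if the results reported scores described as secondary as if they were confirmatory tests, or gave p-values without naming the test used.
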